12.1. Efficacy analysis

12.1.1. Best Overall Response and Objective Response

Best overall response (BOR) will be assessed based on reported overall lesion responses at different evaluation time points from the first dose of SL-901 until the first documentation of PD, according to the following hierarchical rules.

- CR = at least two determinations of CR at least 4 weeks apart and before first documentation of PD
- PR = at least two determinations of PR or better (PR followed by PR or PR followed by CR) at least 4 weeks apart and before first documentation of PD (and not qualifying for a CR)
- SD (applicable only to patients with measurable disease at baseline) or Non-CR/non-PD (applicable only to patients with non-measurable disease at baseline) = at least one SD (or non-CR/non-PD) assessment (or better) \geq 6 weeks after the first dose of SL-901 and before first documentation of PD (and not qualifying for CR or PR).
- SD = unconfirmed CR/PR (i.e. one determination of CR or PR followed by PD or NE) occurring at least 6 weeks after the first dose of SL-901
- PD = at least one documentation of PD (and not qualifying for CR, PR, SD or non-CR/non-PD).
- NE = all other cases.

Objective Response (OR) is defined as confirmed BOR of CR or PR according to RECIST v1.1.

Each patient will have an objective response status (0: no OR; 1: OR).

OR rate (ORR) is the proportion of patients with OR in the relevant analysis set.

Disease Control (DC) is defined as BOR of CR, PR, non-CR/non-PD or SD.

DC rate (DCR) is the proportion of patients with DC in the relevant analysis set.

CR rate (CRR) is the proportion of patients with a confirmed BOR of CR in the relevant analysis set.

ORR, DCR and CRR by cohort and overall will be calculated along with the 2-sided 95% CI using the Clopper-Pearson method (exact CI for a binomial proportion as computed by default by the FREQ procedure using the EXACT option).

In addition, the number and percentage of patients with BOR of CR, PR, SD, non-CR/non-PD (applicable only to patients with non-measurable disease at baseline), PD, and NE will be tabulated.

These analyses will be presented by cohort both in the Efficacy and in the Per Protocol populations.

All data related to target lesions, non-target lesions, new lesions and response assessment will be listed.

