8.5.1. Prohibited Concurrent Medications

The following medications are prohibited during the study:

- Any investigational agent or device other than SL-901, including agents that are commercially available for indications other than the patient's solid tumor that are under investigation for the treatment of solid tumors.
- Any anti-neoplastic treatment with activity against solid tumors other than SL-901.

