8.8. Pharmacokinetics

See [Table 8](#) for the PK assessment schedule.

A large black rectangular box redacting content from the original document.

8.9. **Electrocardiogram**

Twelve-lead ECGs will be performed 5 to 10 minutes before the PK sample is collected and analyzed locally in triplicate over 5 minutes (\pm 5 minutes) contemporaneously with selected PK sampling time points, as indicated in [Table 8](#).

Table 8: Time Points for Pharmacokinetic and Electrocardiogram Assessments

Timepoint	Run-in Serial PK Sampling and ECGs (3-7 days before C1D1; Part 1a only)		Steady State Sampling and ECGs (C1D8; C1D22; C2D1; C2D8; C2D15; C2D22; Cycles 3 and beyond D1, D15 Part 1a and Part 1b)		Serial PK Sampling and ECGs (C1D15 Part 1a and Part 1b)	
	PK	ECG¹	PK	ECG¹	PK	ECG¹
Predose	X	X	X	X	X	X
60 minutes postdose	X	X	--	--	X	X
2 hours postdose	X	X	--	--	X	X
4 hours postdose	X	X	--	--	X	--
6 hours postdose	X	--	--	--	X	--
8 hours postdose	X	--	--	--	X	--
10 hours postdose	X	--	--	--	X	--
12 hours postdose	X	--	--	--	X	--
24 hours postdose	X	X	--	--	X	X
48 hours postdose	X	X	--	--	--	--
72 hours postdose	X	X	--	--	--	--

C = cycle, D = day, ECG = electrocardiogram, PK = pharmacokinetic

¹. ECG should be performed as triplicates and at least 5-10 minutes before the PK sample is collected.

8.10. **Pharmacodynamics**

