9.3.5. Efficacy Analyses

- Response evaluation is based upon the Investigator's determination of response using RECIST v1.1 ([Eisenhauer 2009](#)). A response is defined as instance of a patient exhibiting a confirmed complete response (CR) or partial response (PR).

- Objective response rate (ORR) is defined as the number of patients exhibiting response divided by the number of patients qualified for tumor response analysis.
- Progression-free survival (PFS) is defined as the time from the first study drug dose to the first date of objectively determined disease progression or death from any cause. For patients who are still alive at the time of analysis and without evidence of tumor progression, PFS will be censored at the date of the most recent objective progression-free observation. For patients who receive subsequent anticancer therapy before objective disease progression or death, PFS will be censored at the date of the last objective progression-free observation before the date of subsequent therapy.
- Duration of response (DOR) is defined as the time from the date when the measurement criteria are met for CR or PR (whichever status is recorded first) until the date of first observation of objective disease progression. Duration of response will be censored at the date of the last objective progression-free disease assessment for patients who respond to treatment and die without progressive disease (excluding death from study disease). For responding patients not known to have died at the time of the data analysis and who do not have progressive disease, duration of response will be censored at the last progression-free assessment date. The disease control rate (DCR; CR + PR + stable disease) will be similarly analyzed.

For responding patients who receive subsequent anticancer therapy (after discontinuation from all study treatment) before disease progression, duration of response will be censored at the date of last progression-free assessment before the initiation of post-discontinuation anticancer therapy.

- Duration of CR (DOCR) is defined as the time from the date when the measurement criteria are met for CR until the date of first observation of objective disease progression.
- Overall survival (OS) is defined as the time from the first study drug dose to the date of death from any cause. For patients who are still alive at the time of the analysis, OS time will be censored on the date of the patient's last contact.

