9.3.6. Pharmacokinetic Analysis

9.3.7. *Electrocardiogram Analysis*

The proportions of patients with treatment-emergent clinically significant ECG abnormalities will be tabulated, and changes in ECG findings will be presented in data listing format. If warranted, categorical analyses of QTc interval data will be provided for the number and percentage of patients meeting or exceeding the following threshold values:

- Absolute QTc interval prolongation: QTc interval >450 ms, >480 ms, and >500 ms
- Change from Baseline in QTc interval: QTc interval increases >30 ms and >60 ms

9.3.8. *Pharmacodynamic Analysis*

PD analyses will be described in a separate Statistical Analysis Plan.

9.4. *Changes to the Planned Statistical Methods*

Changes to the planned statistical methods will be documented in the clinical study report.

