12.1.2. Duration of Response

Duration of response (DOR) is defined, for patients with OR, as the time (in months) from the first documentation of objective response (CR or PR) to the date of first documentation of PD.

Duration of Complete Response (DOCR) is defined, for patients with a confirmed BOR of CR, as the time from the first documentation of CR to the date of first documentation of PD.

DOR and DOCR will be calculated as follows:

$$\text{DOR (months)} = [\text{date of event or censoring} - \text{first date of OR} + 1] / 30.4375$$

$$\text{DOCR (months)} = [\text{date of event or censoring} - \text{first date of CR} + 1] / 30.4375$$

DOR and DOCR will be censored at the last tumor assessment if the patient did not have disease progression. If a patient receives a new systemic anti-cancer therapy before disease progression, DOR and DOCR will be censored at the last tumor assessment before the date of initiation of new systemic anti-cancer therapy. In addition, patients who experience PD after ≥ 2 missing tumor assessments will be censored at the last tumor assessments prior to the missed visits.

[figure not shown]
DOR and DOCR will be analyzed by cohort using the Kaplan-Meier method, with the median, 25th and 75th percentiles as well as DOR and DOCR rates at 3, 6 and 12 months (and every 6 months thereafter until the end of follow-up or no more subjects are at risk) reported along with the 2-sided 95% CIs calculated according to Brookmeyer and Crowley using a linear transformation (CONFTYPE=LINEAR in SAS Proc LIFETEST). Number and percentage of patients with event (PD) and censoring reasons will be presented by cohort.

[figure not shown]
DOR and DOCR will be displayed graphically using Kaplan-Meier curves.

These analyses will be presented by cohort both in the Efficacy and in the Per Protocol populations.

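### SAP best overall response has no cut-off at new systemic anti-cancer therapy although duration of response does, so a first response on another drug counts in ORR with a negative DOR

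*SAP*

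**What the plan says.** **Response.** SAP 12.1.1 assesses BOR "from the first dose of SL-901 until the first documentation of PD, according to the following hierarchical rules". CR and PR each need two determinations at least 4 weeks apart, and the only end-point named for either is first PD. OR, ORR, CRR and DCR all derive from this BOR. In Protocol 9.3.5 the definition is: "A response is defined as instance of a patient exhibiting a confirmed complete response (CR) or partial response (PR"). It sets no window and no cut-off at later therapy.

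**Duration.** SAP 12.1.2 computes DOR for every patient with OR, starting at the first documented response. For a patient given another systemic drug before progression, "DOR and DOCR will be censored at the last tumor assessment before the date of initiation of new systemic anti-cancer therapy". Protocol 9.3.5 has a corresponding censoring rule for DOR and one for PFS.

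**Follow-up.** Under Protocol 8.7 and SAP section 12, patients who stop SL-901 for a reason other than progression go on being scanned every 8 weeks (±1 week) until 6 months after first dose, then every 90 days. The visible text does not end these scans when another therapy starts.

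**Other treatment.** Protocol 8.5.1 prohibits the following during the study: "Any anti-neoplastic treatment with activity against solid tumors other than SL-901". SAP 11.3 nevertheless gives imputation rules for the start date of post-treatment systemic anti-cancer therapy.

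**The concern.** The two sections treat the same event differently. A scan taken on another drug can make a patient a responder under 12.1.1, but 12.1.2 does not allow that scan to contribute to duration. When the first response appears only after the new drug starts, two things follow:

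- ORR, and CRR for a complete response, credit SL-901 with a response that arose on a different treatment.
- The DOR censoring date falls before the DOR start date, which is not a valid survival time.

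At 3 to 6 patients per cohort, a single patient visibly changes the reported response rate.

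**Working it through.** The documents give no sample size, power or event figure that bears on this point, so there is no stated figure to reproduce. The check applies the SAP rules to a patient who follows the visit schedule.

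**Inputs**

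- DOR formula (SAP 12.1.2): (event or censoring date - first OR date + 1)/30.4375.
- Run-in dose (Protocol Table 8): "Run-in Serial PK Sampling and ECGs (3-7 days before C1D1; Part 1a only").
- Cycle length 28 days; scan after every 2 cycles; off-treatment scans every 8 weeks (±1 week).
- Cohort size 3 to 6, at most 60 patients in Part 1a (Protocol 9.1, SAP section 8).
- ORR interval: two-sided 95% Clopper-Pearson, by cohort and overall (SAP 12.1.1).
- Assumed: the patient's response pattern, and a new-therapy start on day 88. Any start after the day-60 scan and before the day-116 scan gives the same result.

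**Timeline.** Take first dose as day 1. C1D1 then falls on day 4 to 8, and two cycles later is day 4 + 56 = 60 to 8 + 56 = 64. The next 8-weekly scans fall on days 116-120 and 172-176, all before 6 x 30.4375 = 182.6 days.

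**Case A: first response after the new therapy.** SD on day 60, SL-901 stopped, new systemic therapy on day 88, PR on days 116 and 172, no PD.

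- The two PRs are 172 - 116 = 56 days apart (at least 28 required) and precede any PD, so BOR = PR and OR = 1.
- The last scan before new therapy is day 60 and the first OR date is day 116. DOR = (60 - 116 + 1)/30.4375 = -55/30.4375 = -1.81 months.

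| Gap, last scan before new therapy to first response (days) | DOR (months) |
|---|---|
| 1 | 0.00 |
| 49 | -48/30.4375 = -1.58 |
| 56 | -55/30.4375 = -1.81 |
| 63 | -62/30.4375 = -2.04 |
| 90 | -89/30.4375 = -2.92 |

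Any gap longer than 1 day gives a negative value, so the sign does not depend on the example dates.

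With a cut-off at new therapy, only the day-60 scan counts. It is more than 6 weeks after first dose, so BOR = SD. The patient leaves ORR and has no DOR record, and DCR is unchanged.

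**Case B: only the confirmation after the new therapy.** PR on day 60, new therapy on day 88, PR again on day 116. BOR = PR and DOR = (60 - 60 + 1)/30.4375 = 0.03 months (1 day), censored. That is a valid time. With the cut-off, the PR is unconfirmed and BOR = SD.

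**Effect of one such patient on ORR**

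| Denominator | Without the patient's response (95% CI) | With it (95% CI) |
|---|---|---|
| 3 | 0/3 = 0% (0 to 70.8%) | 1/3 = 33.3% (0.8 to 90.6%) |
| 6 | 0/6 = 0% (0 to 45.9%) | 1/6 = 16.7% (0.4 to 64.1%) |
| 60 (ceiling) | 0/60 = 0% (0 to 6.0%) | 1/60 = 1.7% (0.0 to 8.9%) |

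The study stopped early (SAP section 4), so the real overall denominator may be below 60 and the overall shift correspondingly larger than 1.7 points.

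**The case against.** **The route is narrow.** Other anti-neoplastic treatment is prohibited during the study, and Protocol 5.1 admits only patients without an effective standard option. The patient must stop SL-901 before progression, start another systemic drug, keep being scanned, respond for the first time on that drug, and have it confirmed at least 4 weeks later before PD. This stands as a limit on frequency. It does not close the gap, because Protocol 9.3.5 and SAP 11.3 and 12.1.2 all provide for therapy before progression or after treatment.

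**RECIST v1.1 may supply the cut-off.** SAP 12.1.1 cites RECIST but writes out its own window, and that window is what would be programmed. What RECIST itself adds cannot be checked from these documents, so this lowers certainty a little without answering the point.

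**The error would show itself.** A negative DOR would appear in the by-patient DOR listing (Listing 16.2.6.4). That is true of Case A. The 1-day value in Case B may not stand out, but Case B is the weaker case: the response was first seen before the new drug, and the documents do not settle whether a later scan may confirm it.

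**Stronger readings that the documents do not support.**

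- A reader might infer that the SAP departs from the Protocol on response. It does not, since the Protocol definition has no cut-off either.
- A reader might infer that DOR is inflated. This mismatch gives negative or very short values and does not lengthen DOR.
- A reader might infer an unlisted SAP change on death from the study disease. Protocol 9.3.5 censors DOR for responders who "die without progressive disease (excluding death from study disease"), while the SAP says "DOR and DOCR will be censored at the last tumor assessment if the patient did not have disease progression". But both documents end DOR at objective progression, and the Protocol never makes such a death an event. A figure is also missing directly after the SAP censoring text, and the visible text does not show that cause of death is collected. No deviation can be shown.

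**Conclusion.** The point holds as a minor inconsistency within the SAP. As written, a confirmed first response on another systemic drug counts in ORR or CRR, and its DOR is negative: -1.8 months in the example, and -1.6 to -2.0 months for gaps of 49 to 63 days. One such patient adds 33 points to ORR in a cohort of 3, 17 points in a cohort of 6, and 1.7 points overall at 60 patients.

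This rests on the visible text of SAP 12.1.1, where no figure is marked missing, and on the assumption that such a patient exists. The documents give no frequency, and it may be zero. Clinical activity is a secondary, descriptive endpoint, no decision rule uses it, and Part 1b was not started.

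**What to change.** In SAP 12.1.1, state that BOR uses only assessments, including the confirming one, made up to first documented PD and before the start of any new systemic anti-cancer therapy, whichever comes first. Use the same therapy definition as 12.1.2, and apply the rule to BOR, ORR, CRR and DCR.

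The cost is one sentence. The therapy start date is already needed for DOR censoring and already has imputation rules in SAP 11.3. The downside is that ORR, CRR or DCR may be slightly lower, and a Case B patient would be reclassified from PR to SD.

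The SAP is to be finalised before database lock, so the change belongs there. If that point has passed, Protocol 9.4 gives the route: "Changes to the planned statistical methods will be documented in the clinical study report".

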12.1.2. Duration of Response

Duration of response (DOR) is defined, for patients with OR, as the time (in months) from the first documentation of objective response (CR or PR) to the date of first documentation of PD.

Duration of Complete Response (DOCR) is defined, for patients with a confirmed BOR of CR, as the time from the first documentation of CR to the date of first documentation of PD.

DOR and DOCR will be calculated as follows:

$$\text{DOR (months)} = [\text{date of event or censoring} - \text{first date of OR} + 1] / 30.4375$$

$$\text{DOCR (months)} = [\text{date of event or censoring} - \text{first date of CR} + 1] / 30.4375$$

DOR and DOCR will be censored at the last tumor assessment if the patient did not have disease progression. If a patient receives a new systemic anti-cancer therapy before disease progression, DOR and DOCR will be censored at the last tumor assessment before the date of initiation of new systemic anti-cancer therapy. In addition, patients who experience PD after ≥ 2 missing tumor assessments will be censored at the last tumor assessments prior to the missed visits.

[figure not shown]
DOR and DOCR will be analyzed by cohort using the Kaplan-Meier method, with the median, 25th and 75th percentiles as well as DOR and DOCR rates at 3, 6 and 12 months (and every 6 months thereafter until the end of follow-up or no more subjects are at risk) reported along with the 2-sided 95% CIs calculated according to Brookmeyer and Crowley using a linear transformation (CONFTYPE=LINEAR in SAS Proc LIFETEST). Number and percentage of patients with event (PD) and censoring reasons will be presented by cohort.

[figure not shown]
DOR and DOCR will be displayed graphically using Kaplan-Meier curves.

These analyses will be presented by cohort both in the Efficacy and in the Per Protocol populations.

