3.1. Changes from study protocol

Since the PK run-in period is included in the DLT assessment period, the DLT population definition has been modified so that in order to be considered DLT evaluable a patient must have taken also the full dose during the run-in period in addition to at least 75% of the planned SL-901 doses in Cycle 1.

4. Study overview

SL-901 is an orally bioavailable investigational anticancer drug aimed to treat patients whose cancers harbor an overactive phosphoinositide 3-kinase (PI3K) signaling.

This is a Phase I, open-label, dose-escalation and cohort expansion study in two parts: In Part 1a, escalating doses and 2 schedules of SL-901 will be evaluated in patients with advanced solid tumors, to identify the maximum tolerated dose (MTD) and determine the regimen for Part 1b. In Part 1b, the clinical activity of SL-901 at the selected dose and schedule will be further characterized in patients with advanced solid tumors known to have specific genetic alterations and who may derive benefit from treatment with a PI3K inhibitor.

The study was stopped early and Part 1b was not started.

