12.1.3. Progression-free survival

Progression-free survival (PFS) is defined as the time (in months) from the date of first intake of SL-901 to the date of the first documentation of PD (per RECIST v1.1) or death due to any cause, whichever occurs first, regardless of whether the patients withdraws from study treatment.

PFS will be analyzed by cohort and overall using the Kaplan-Meier method, with the median, 25th and 75th percentiles as well as PFS rates at 3, 6 and 12 months (and every 6 months thereafter until the end of follow-up or no more subjects are at risk) reported along with the 2-sided 95% CIs calculated according to Brookmeyer and Crowley using a linear transformation (CONFTYPE=LINEAR in SAS Proc LIFETEST). Number and percentage of patients with each event type (PD or death) and censoring reasons will be presented by cohort.

PFS will be displayed graphically using Kaplan-Meier curves.

These analyses will be presented by cohort both in the Efficacy and in the Per Protocol populations.

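### SAP 12.1.2 drops, without declaring it, the protocol's exception that keeps deaths from study disease out of DOR censoring

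*SAP*

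**What the plan says.** **SAP 12.1.2.** DOR and DOCR both run to the first documented progression (PD). The censoring sentence is "DOR and DOCR will be censored at the last tumor assessment if the patient did not have disease progression", with no carve-out for deaths. The planned output matches: "Number and percentage of patients with event (PD) and censoring reasons will be presented by cohort". PD is the only event type.

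**Protocol 9.3.5, DOR.** The definition also ends at objective progression: "until the date of first observation of objective disease progression. Duration of response will be censored". Censoring at the last progression-free assessment then applies to patients who "die without progressive disease (excluding death from study disease" (the parenthesis closes there). The next censoring sentence covers only responders not known to have died. Apart from the subsequent-therapy rule, nothing in the section censors a responder who dies of the study disease.

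**Protocol 9.3.5, DOCR.** The endpoint is given only as the time from when "criteria are met for CR until the date of first observation of objective disease progression". No rule for deaths follows.

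**PFS.** SAP 12.1.3 counts progression or "death due to any cause, whichever occurs first". Protocol 9.3.5 also counts death from any cause.

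**SAP 3.1.** The only listed change from the protocol is that "the DLT population definition has been modified".

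**The concern.** The SAP presents itself as giving further detail on the protocol's methods, and it has a section for departures. A reader who finds only the DLT change there will assume that the protocol's DOR rule still applies. It does not: the exception for death from study disease has gone.

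Kaplan-Meier censoring assumes that a censored patient has the same future risk as those still under observation. A responder who dies of the cancer between two scans is the patient for whom that is least credible, because the death is itself evidence that disease control had ended. Scans are every two 28-day cycles on treatment. For patients off treatment without progression, they move to every 90 days after month 6. An undocumented progression followed by death is therefore plausible. At stake is an upward bias in a secondary, descriptive measure of clinical activity, produced by a rule that the protocol does not contain.

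**Working it through.** The documents give no expected DOR, event count or response rate, so there is no planned figure to reproduce. The check sets the rules side by side and then illustrates the size.

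**1. Treatment of a responder with no documented PD and no new anticancer therapy**

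| Status | Protocol DOR | SAP DOR | Protocol DOCR | SAP DOCR | PFS, both documents |
|---|---|---|---|---|---|
| Alive | censored | censored | not stated | censored | censored |
| Died, not of study disease | censored | censored | not stated | censored | event |
| Died of study disease | exempt from censoring | **censored** | not stated | censored | event |

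The two documents conflict in one cell: DOR, death from study disease. The protocol does not say in words that such a death is an event, but an exemption from censoring has no other workable meaning.

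**2. Illustration under constant hazards.** All inputs are assumptions:
- f = share of terminal events among responders (PD or death, whichever is first) that are deaths without PD
- g = share of those deaths that are from study disease
- λ = total hazard

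The SAP rule estimates the PD hazard alone, (1−f)λ. The protocol rule adds study-disease deaths, giving (1−f+gf)λ. Medians are inversely proportional to hazards, so

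median under SAP rule / median under protocol rule = (1−f+gf)/(1−f) = 1 + gf/(1−f).

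| f | g = 0 | g = 0.5 | g = 1 |
|---|---|---|---|
| 10% | 1.000 | 1 + 0.05/0.90 = 1.056 | 1 + 0.10/0.90 = 1.111 |
| 20% | 1.000 | 1 + 0.10/0.80 = 1.125 | 1 + 0.20/0.80 = 1.250 |
| 30% | 1.000 | 1 + 0.15/0.70 = 1.214 | 1 + 0.30/0.70 = 1.429 |

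The g = 1 column equals 1/(1−f). That is also the ratio of the SAP rule to a rule counting death from any cause. Against the protocol rule it is an upper bound.

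**3. Simulation check.** 40,000 responders, 8-weekly scans, assumed median time to PD or death of 6 months, f = 20%, g = 50%. The 6-month DOR rate was 59.3% under the SAP rule, 55.6% under the protocol rule and 52.2% with any death as an event. The SAP-protocol gap is 59.3 − 55.6 = 3.7 points. The formula gives 0.5^0.8 − 0.5^0.9 = 57.4% − 53.6% = 3.8 points. Simulated levels are slightly higher because PD is seen only at the next scan. With g = 0 the SAP and protocol rates were identical (59.5%).

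**4. Scale.** Part 1b was not started, so only Part 1a responders contribute, from at most 60 planned patients. At assumed response rates of 5%, 10% and 20%, 60 patients give 3, 6 and 12 responders. A six-patient cohort has at least one responder with probability 1−0.95^6 = 26%, 1−0.90^6 = 47% and 1−0.80^6 = 74%. If a cohort's only responder dies of the cancer without documented PD, the SAP reports no event and no estimable median; the protocol rule, as implied, reports one event.

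**5. Direction.** Changing such a death from an event to a censored observation removes a downward step, so the expected shift is upward. One qualification applies in small samples. Because censoring is back-dated to the last scan, the patient also leaves the risk set for other responders' events between that scan and the death. With irregular scan dates, a single curve could dip locally.

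**The case against.** The strongest reply is that the SAP follows the protocol almost entirely. Both documents define DOR to objective progression, and both censor responders who die of other causes. The exception is a parenthesis that neither names death as an event nor dates it. This is fair as a description, but the parenthesis must do something, and under the SAP text it does nothing. Nor does it help that SAP section 3 cites protocol version 2.0, since it also takes in subsequent amendments.

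Three stronger readings are tempting, and the documents do not support them:
- A reader might infer that censoring deaths in DOR is contrary to the protocol in general. It is not: deaths from other causes are censored in both.
- A reader might infer a contradiction on DOCR. The protocol has no DOCR death rule to contradict; this is a gap that the SAP fills without comment.
- A reader might infer that the SAP's DOR clashes with its own PFS. The same difference stands in the protocol. Aligning the two is a reasonable preference, not the repair of an SAP inconsistency.

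It also stands that the consequence is limited. DOR is secondary and descriptive, and the expansion part did not open. Censoring reasons are tabulated, and DOR, DOCR and survival are listed by patient, so such deaths can be traced. Traceability does not correct the estimate. Finally, figures near the censoring paragraph were not available in the text examined. A censoring table there could add detail, though one restoring the exception would contradict the visible wording.

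**Conclusion.** The point holds in a narrow form. For DOR, SAP 12.1.2 drops the protocol's exception for death from study disease, and SAP 3.1 does not say so. The likely direction is upward. Under constant hazards and assumed shares, the SAP median is 1.00 to 1.11, 1.00 to 1.25 and 1.00 to 1.43 times the protocol median for f = 10%, 20% and 30%, where the range reflects g from 0 to 1. The upper ends require every death without PD to be from study disease. It would go too far to say that reported DOR is overstated: that depends on whether any responder dies this way, which the documents do not tell us, and if none does, the two rules give the same result.

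**What to change.** In SAP 12.1.2:
- Count death from study disease without prior documented PD as a DOR event at the date of death, as the protocol exception implies. Keep censoring for other deaths.
- Apply the same rule to DOCR and state it, since the protocol is silent.
- State how this event ranks against the existing censoring for new therapy and for missed assessments.
- Add a sensitivity analysis for DOR and DOCR with death from any cause as an event, as PFS does. This one needs no attribution of cause of death.

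In SAP 3.1, list any departure from the protocol that remains, including the DOCR rule as an addition. If the sponsor prefers to keep censoring all deaths, that must be declared there.

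The cost is SAP wording and a small amount of programming. The cause of each responder's death must be classified, ideally before database lock and under a stated rule, because the visible SAP text has none. Reported DOR may be slightly shorter.

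### SAP 12.1.2 drops the protocol's progression-free condition from DOR censoring, so that, read literally, a not-evaluable scan can set the censoring date (low priority)

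*SAP*

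**What the plan says.** SAP 12.1.2 has three sentences that set a censoring date for DOR and DOCR:

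- No progression: "DOR and DOCR will be censored at the last tumor assessment if the patient did not have disease progression".
- New systemic therapy before progression: "DOR and DOCR will be censored at the last tumor assessment before the date of initiation of new systemic anti-cancer therapy".
- Progression after a gap: "patients who experience PD after ≥ 2 missing tumor assessments will be censored at the last tumor assessments prior to the missed visits".

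None of them puts a condition on the result of the assessment used.

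Protocol 9.3.5 covers three situations for DOR, and each has the condition:

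- Responder who dies without progression (death from the study disease excepted): "Duration of response will be censored at the date of the last objective progression-free disease assessment for patients who respond to treatment".
- Responder not known to have died and without progression: "duration of response will be censored at the last progression-free assessment date".
- Subsequent therapy: "duration of response will be censored at the date of last progression-free assessment before the initiation of post-discontinuation anticancer therapy".

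For DOCR the protocol gives only a definition, which begins "Duration of CR (DOCR) is defined as the time from the date when the measurement criteria are met for CR". It gives no censoring rule for that endpoint.

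SAP 3.1, on changes from the protocol, lists only the revised DLT population.

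**The concern.** A scan read as NE does not show that the patient is free of progression. If it sets the censoring date, the patient stays in the Kaplan-Meier risk set over an interval in which progression status was not observed. The larger risk set can only raise the estimated curve. NE is a result the SAP foresees: SAP 12.1.1 allows for "one determination of CR or PR followed by PD or NE". The tumor-assessment rules in SAP 11.3 do not close the gap, because they choose the censoring date by whether a date is available and say nothing on evaluability. A programmer working from the readable text would take the latest assessment date. At stake is a secondary, descriptive endpoint analyzed by cohort, where one patient can carry noticeable weight.

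**Working it through.** The plan states no figure to reproduce: there is no formal sample size, expected DOR or expected number of responders. The check compares the two rules and then follows the consequence through the Kaplan-Meier arithmetic.

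**Where the rules differ.** The first two SAP sentences apply only before progression, so the last assessment they pick is never a progression. It is either evaluable and progression-free, in which case both rules give the same date, or it is NE, in which case they differ.

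**Shift for one patient.** Inputs: tumor assessment every 2 cycles of 28 days (SAP 5.2 and 12), so 2 × 28 = 56 days; off treatment without progression, every 8 weeks (also 56 days) to 6 months after first dose, then every 90 days (SAP 12); 30.4375 days per month (SAP 7.2.1).

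- One trailing NE on the 56-day schedule: 56 / 30.4375 = 1.84 months.
- One trailing NE on the 90-day schedule: 90 / 30.4375 = 2.96 months.

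Illustration with assumed days, using the SAP's DOR formula: PR on day 63, PR on day 119, NE on day 175, then off study. The protocol rule censors at (119 − 63 + 1) / 30.4375 = 1.87 months. The literal SAP rule censors at (175 − 63 + 1) / 30.4375 = 3.71 months. These are one patient's censoring times, not estimates of DOR.

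**Effect on the curve.** The estimate is the product of (1 − d/n) over event times, with d events among n at risk. Moving one censoring time from c₁ to c₂ raises n to n + 1 at event times after c₁ and up to c₂, and changes nothing else. Each affected factor becomes 1 − d/(n + 1), which is larger. The effect is therefore zero or upward, and is zero unless another responder progresses after c₁ and no later than c₂.

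Three assumed datasets show this. Times are visit numbers on the 56-day grid, with 1 visit = 1.84 months. The +1 day in the SAP formula is left out; it would add 0.03 months to every time. The median is the first time the estimate is at or below 0.5.

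| Case | Events at visits | Other censored at visits | Moved patient | Last evaluable | NE date |
|---|---|---|---|---|---|
| A, 6 responders | 2, 5, 6 | 7, 8 | 3 → 4 | 0.833, 0.625, 0.417; median 11.04 months | identical |
| B, 6 responders | 2, 4, 5, 6 | 8 | 3 → 4 | 0.833, 0.625, 0.417, 0.208; median 9.20 | 0.833, 0.667, 0.444, 0.222; median 9.20 |
| C, 3 responders | 2, 3 | none | 1 → 2 | 0.500, 0; median 3.68 | 0.667, 0; median 5.52 |

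In B the change enters at visit 4: (5/6)(1 − 1/4) = 0.625 against (5/6)(1 − 1/5) = 0.667. In C it enters at visit 2: 1 − 1/2 = 0.500 against 1 − 1/3 = 0.667. The first median in C falls where the estimate equals 0.5 exactly; a midpoint convention would give (3.68 + 5.52) / 2 = 4.60 months in its place.

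**Range under assumed rates.** Assumptions, none from the documents: exponential time to progression with median 6 months, scans every 56 days, 100,000 simulated responders. The 6-month DOR rate under the literal SAP rule exceeds that under the protocol rule by:

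| Drop-out per visit | 10% NE scans | 20% NE scans |
|---|---|---|
| 10% after any scan | 0.4 points | 0.9 points |
| 60% after NE, 10% after evaluable | 2.3 points | 5.0 points |

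With the less favorable drop-out pattern and 10% NE, the 3-, 6- and 12-month estimates were identical under both rules in 89% of samples of 3 responders and 62% of samples of 6.

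**The case against.** The strongest reply is that the SAP wording is shorthand. The SAP presents itself as giving further detail on the protocol's methods, already excludes progression from the censoring sentence, and lists no change to DOR in section 3.1. On that view the protocol's condition still applies. This is a fair reading of intent, but it does not settle what is programmed: the readable sentences state a rule, and that rule differs from the protocol's.

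Three stronger readings are tempting, and the documents do not support them.

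- *The SAP provides for NE scans to set the date.* It does not say so. This follows from an unqualified phrase. The NE wording in SAP 12.1.1 shows only that NE is a possible result; it concerns unconfirmed responders classed as SD, who do not enter the DOR analysis.
- *DOR is therefore overstated.* Case A shows no effect and case B an unchanged median. Any size depends on NE and drop-out rates that the documents do not give; the simulated gap falls below 1 point when drop-out does not depend on evaluability.
- *The SAP contradicts the protocol on DOCR.* The protocol has no DOCR censoring rule to contradict. The ambiguity reaches DOCR only because the same SAP sentences govern both endpoints.

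A figure is missing from the readable copy after the censoring sentences and might define an adequate assessment. If so, those sentences would still need to agree with it. It is also true that the SAP plans by-patient listings of tumor response and DOR, so an NE-driven date would be visible, and that few cohorts are likely to have several responders. Both points lower the priority; neither makes the rule match the protocol.

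**Conclusion.** The point holds as a departure in wording with a conditional consequence. SAP 12.1.2 omits the progression-free condition that Protocol 9.3.5 applies to DOR in all three of its situations, and SAP 3.1 does not declare the change. Taken literally, each trailing NE visit delays that patient's censoring by 1.84 or 2.96 months, depending on the schedule. The resulting bias in the curve is upward or nil. The shifts rest on the documents' own schedule and month length; the size of the bias rests on assumptions alone. Cohorts of 3 to 6 patients (SAP 8), the early stop and the unstarted Part 1b (SAP 4) make a material effect unlikely. This is a low-priority correction.

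**What to change.** In the censoring sentences of SAP 12.1.2, make the reference date the last evaluable tumor assessment showing no progression (CR, PR, SD or non-CR/non-PD). For DOR this matches Protocol 9.3.5; for DOCR it is a choice made for consistency and should be described as such. State whether an NE assessment counts as missing under the rule for two or more missed assessments. Use the same condition in the tumor-assessment censoring rules of SAP 11.3. If NE dates are meant to count, list that in SAP 3.1 with the reason.

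The cost is a few words and one filter in the program, settled before database lock. Patients with a counted progression, or whose last assessment is evaluable, keep the same DOR; reported DOR may become slightly shorter.
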